13.2 Statistical analysis plan

Patient and imaging characteristics will be summarized and compared using appropriate summary statistics, e.g. mean and standard deviation for continuous variables, frequency and percentage for categorical variables, and extensive exploratory data analysis and data visualizations will be utilized to assess diagnostics, identify outliers, and validate assumptions.

Receiver operating characteristic (ROC) analysis will be used in Aim 1 to estimate the accuracy of DECT for differentiating no varices from any varices and for differentiating no and small varices from large varices in Aim 1. Sensitivity, specificity, accuracy, and AUC along with their two-sided 95% CI will be presented separately. The grade of varices (0, 1, 2) on DECT will be correlated with the grade of varices on endoscopy (0, 1, 2) using weighted Kappa coefficient for categorical data (Aim 2.2).

The MIXED effect model will be used in Aim 2.1 to estimate the ICC for the inter-observer agreement for the detection of any varices and high-risk varices on dual energy CT. Reader experience and subject will be the two random effects in the model used for interobserver variability. The intraclass correlation coefficient (ICC) will be defined as the ratio between subject variance and the sum of variances for subject, reader experience and error term. ICC values will be characterized as very poor (0 to <0.20), poor (0.20 to <0.40), moderate (0.40 to <0.60), good (0.60 to <0.80), and very good (0.80 to 1.00).

Time to development of bleeding varices (or hepatic event) will be modeled in Aim 2.3 using Cox proportional hazards models with clustered sandwich estimators to account for within and between cluster correlations. Cause specific proportional subhazards analysis while accounting for competing risks (e.g. gastroesophageal banding) and adjusting for covariates will be utilized to assess the association between endoscopic findings and DECT findings and time to developing individual vs. any hepatic complications.

A combination of variceal grade on DECT, LSN score and MELD score will have equal or greater accuracy for predicting 2-year liver-related events than a combination of endoscopic findings and MELD score. This analysis will be exploratory in Aim 2.4, but a trend may be evident and justify further investigation. Competing risks analysis will be used to assess the association of variceal grade on DECT, LSN score and MELD scores with development of liver-related events, with specific attention to 2-year variceal bleeding events. Cumulative Incidence Function (CIF) will be used to estimate the marginal probability of a liver-related event as a function of its cause-specific probability and overall survival probability.

All analysis will be carried out using SAS v 9.4.

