3.2 Secondary Objectives

- 3.2.1** To assess inter-observer agreement for the detection of any varices and high-risk varices on dual energy CT.
- 3.2.2** To compare the accuracy of grade of varices on CT to grade of varices on endoscopy for predicting gastroesophageal variceal bleeding at 2 years.
- 3.2.3** To develop and compare the accuracy of multivariate statistical models designed to predict 2-year risk of bleeding gastroesophageal varices, both without and with dual energy CT findings.
- 3.2.4** To predict 2-year liver-related events using the variceal grade on DECT, LSN score and MELD score.

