13.1 Sample size justification

[name] (co-investigator and biostatistician) will conduct and supervise all statistical analyses. This is a prospective study to determine the accuracy of dual energy CT for detecting any varices and high-risk varices in patients with cirrhosis presenting for upper gastrointestinal endoscopy. The endpoint of the primary objective is accuracy which is determined by the Area Under the Curve (AUC) using Recursive Operating Characteristics (ROC) analysis (AUROC). Based on published studies ^{1,2,3} in patients with detected gastroesophageal varices, we will observe 32%, 32%, and 36% with no, small, and large varices, respectively. In order to test the hypothesis: the accuracy (AUROC) of DECT will be >0.90 for detecting any and high-risk varices in a prospective pilot study that uses endoscopy as the reference standard, we plan to enroll 50 patients such that we will have 16/50, 16/50, and 18/50 with no, small, and large varices. This size of the study will have $>95\%$ power to detect any varices, e.g. (16+18)/50 small and large varices with $AUC >=0.90$ comparing to null hypotheses of $AUC=0.5$ (not detect any) using a one-sided z-test at a significance level of 0.05 controlled false positive rates at 1%.

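### Objective 3.2.2 asks which grade, CT or endoscopy, better predicts 2-year variceal bleeding, but its assigned analysis (Aim 2.2) is a weighted kappa that does not use bleeding

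*Combined protocol and SAP*

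**What the plan says.** Section 3.2, objective 3.2.2: "To compare the accuracy of grade of varices on CT to grade of varices on endoscopy for predicting gastroesophageal variceal bleeding at 2 years".

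Section 13.2, in the same paragraph as the Aim 1 ROC analyses, says that the grade "on DECT will be correlated with the grade of varices on endoscopy (0, 1, 2) using weighted Kappa coefficient for categorical data (Aim 2.2"). This is the only analysis labelled Aim 2.2.

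Other text in section 13 that bears on the point:

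- **AUC** is tied to the primary objective in section 13.1: "The endpoint of the primary objective is accuracy which is determined by the Area Under the Curve (AUC"). In section 13.2, ROC analysis is assigned to Aim 1 only.
- **Aim 2.3** uses Cox models for time to bleeding or a hepatic event. The text then plans "Cause specific proportional subhazards analysis while accounting for competing risks (e.g. gastroesophageal banding) and adjusting for covariates", used "to assess the association between endoscopic findings and DECT findings and time to developing individual vs. any hepatic complications".
- **Aim 2.4** (exploratory) hypothesises that DECT grade, LSN score and MELD score together "will have equal or greater accuracy for predicting 2-year liver-related events than a combination of endoscopic findings and MELD score". Its method sentence is "Competing risks analysis will be used to assess the association of variceal grade on DECT, LSN score and MELD scores" with liver-related events, and it singles out 2-year variceal bleeding.

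Objective 3.2.3, a related but smaller matter, is "To develop and compare the accuracy of multivariate statistical models designed to predict 2-year risk of bleeding gastroesophageal varices", without and with DECT findings.

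**The concern.** The objective asks about prediction of an outcome, and the method labelled for it contains no outcome. Kappa is also symmetric in the two grades: swapping CT and endoscopy leaves it unchanged, so it cannot say which predicts better.

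Two things are at stake. The only result labelled for 3.2.2 would be an agreement figure, and a high kappa could be read as showing that CT predicts bleeding as well as endoscopy does. If instead an accuracy comparison is added when the 2-year data are in hand, the measure, the handling of competing events and the choice of controls would all be open at that point. Section 12 calls detection of bleeding a critical part of the study, and patients are followed for 2 years to obtain it, so the comparison deserves a defined analysis.

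Separately, 3.2.3 promises to compare the accuracy of models, but no time-to-event accuracy measure and no optimism correction is stated. That is missing detail and does not carry this point.

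**Working it through.** **1. Does Aim 2.2 correspond to objective 3.2.2?** The other labels follow the objectives in order.

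| Objective | Subject | Label in 13.2 | Method |
|---|---|---|---|
| 3.2.1 | Inter-observer agreement | Aim 2.1 | Mixed model, ICC |
| 3.2.2 | CT vs endoscopy grade, accuracy for 2-year bleeding | Aim 2.2 | Weighted kappa between grades |
| 3.2.3 | Bleeding models without and with DECT | Aim 2.3 | Cox and competing-risk models |
| 3.2.4 | Liver-related events from DECT grade, LSN, MELD | Aim 2.4 | Competing risks, cumulative incidence |

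If the label was misplaced and kappa belongs with Aim 1, then 3.2.2 has no labelled analysis. The gap exists on either reading.

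**2. Do Aims 2.3 or 2.4 supply the comparison?** Aim 2.3 estimates covariate-adjusted association and names no accuracy measure. The Aim 2.4 hypothesis concerns all liver-related events and puts LSN on the DECT side only, so a difference could come from LSN. Its method sentence names only the DECT-side predictors.

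**3. Kappa against predictive accuracy.** The plan gives no figure for 3.2.2 to reproduce; its only power statement concerns the primary objective. From section 13.1 I take 50 patients with margins 16/16/18. The rest is assumed: 8 patients discordant between grades 1 and 2 (4 each way), giving cells (endoscopy, CT) of (0,0)=16, (1,1)=12, (2,2)=14, (1,2)=4, (2,1)=4; and 5 bleeds, 3 of them large on both tests.

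Weighted kappa = 1 - (observed weighted disagreement)/(expected weighted disagreement).

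- Linear: observed 8×0.5/50 = 0.08. Expected (2×16×16×0.5 + 2×16×18×0.5 + 2×16×18×1)/2500 = 1120/2500 = 0.448. Kappa = 1 - 0.08/0.448 = 0.82.
- Quadratic: 0.04 and 848/2500 = 0.3392. Kappa = 0.88.

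Bleeding enters neither formula. AUC for bleeding is the share of bleeder/non-bleeder pairs ranked correctly, with ties counted as half. If the other 2 bleeders are large on CT only:

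- CT: all 5 bleeders are large; the 45 non-bleeders are 16 none, 16 small, 13 large. AUC = (32 + 6.5)/45 = 0.86.
- Endoscopy: 3 bleeders are large and 2 small; non-bleeders are 16, 14, 15. AUC = [3×(30 + 7.5) + 2×(16 + 7)]/(5×45) = 158.5/225 = 0.70.

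| Other 2 bleeders | Linear kappa | AUC CT | AUC endoscopy | Difference (DeLong 95% CI) |
|---|---|---|---|---|
| Large on CT only | 0.82 | 0.86 | 0.70 | +0.15 (-0.02 to 0.32) |
| One each way | 0.82 | 0.78 | 0.78 | 0 (-0.21 to 0.21) |
| Large on endoscopy only | 0.82 | 0.70 | 0.86 | -0.15 |

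For the first row the DeLong SE is 0.085, and a patient bootstrap gives 0.00 to 0.34.

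**4. Precision.** By the Hanley-McNeil variance at AUC 0.75 and n=50, the 95% half-width for one AUC is 0.26 with 5 bleeds and 0.19 with 10. The documents give no bleeding rate, so both counts are assumptions.

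**5. Treatment triggered by the endoscopic grade.** Using the same table, assume two equally good grades with untreated 2-year risks of 2%, 8% and 25%, and 16.5% in discordant patients. Expected bleeds are 16×0.02 + 12×0.08 + 14×0.25 + 8×0.165 = 6.1, and each grade has AUC 0.72. Now let a share of endoscopy-large patients be banded at random soon after endoscopy, as a competing event.

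| Share banded | CT / endoscopy, event-free controls | CT / endoscopy, all non-bleeders as controls | Expected bleeds |
|---|---|---|---|
| 50% | 0.74 / 0.74 | 0.67 / 0.64 | 4.0 |
| 90% | 0.73 / 0.71 | 0.59 / 0.50 | 2.4 |
| 100% | 0.71 / 0.68 | 0.55 / 0.42 | 1.9 |

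If instead beta blockers halve the risk in endoscopy-large patients, the AUCs are 0.67 and 0.64 under either rule.

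**6. Objective 3.2.3 (smaller point).** In simulated Cox models (n=50, two base predictors, assumed 2-year bleeding rates of 10% to 40%), adding an uninformative DECT grade raises the mean apparent C-index by about 0.01 to 0.08, when the true gain is 0.

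**The case against.** The strongest reply is that the gap is narrow. Aims 2.3 and 2.4 already bring together both sets of findings, bleeding, and banding as a competing event; what is missing is an accuracy measure and a paired comparison. This is also a secondary objective in a 50-patient pilot, and the proposed estimate is unlikely to settle which grade is better: both intervals computed above include zero. Treatment that follows the endoscopic grade, which section 2 leads one to expect, can make two equally good grades look different.

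Much of this stands as a limit on what the comparison can deliver. It does not supply the missing analysis. Neither aim yields grade against grade on accuracy for bleeding, and low precision is a reason to label the result exploratory, not to report agreement in its place. Distortion by treatment strengthens the case for fixing the rule in advance: with 90% banded, the choice of controls alone moves the spurious CT advantage from about 0.02 to 0.09.

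Three narrower points are fair. The illustration is constructed and shows only that kappa ignores outcome. A comparison added later need not be data-driven if it is written down before the 2-year outcomes are analysed. And the follow-up variables do not name beta blockers. Section 2 counts them as treatment for high-risk varices and the interviews ask about such treatment, so they are plausibly captured, but this should be confirmed.

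**Conclusion.** The point holds. As written, the plan has no analysis that answers objective 3.2.2, and the one labelled for it answers a different question. This follows from the text and needs no assumed number.

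The illustration gives the scale: one kappa is compatible with AUC differences of about 0.15 in either direction. It rests on assumed discordance and an assumed 5 bleeds. The point should be fixed, but it touches a secondary objective only; the primary accuracy analysis against endoscopy is unaffected.

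**What to change.** In section 13.2:

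- Keep weighted kappa, described as agreement between the two grades and detached from 3.2.2.
- For 3.2.2, estimate the 2-year time-dependent AUC for variceal bleeding for each grade in the same patients, with variceal intervention, TIPS, transplant and death as competing events. Name this one measure; a C-index is not in itself a 2-year quantity.
- State the control rule. For example, use patients free of bleeding and competing events at 2 years as the main rule, with all non-bleeders as a sensitivity analysis.
- Report the paired difference, CT minus endoscopy, with a bootstrap 95% CI, labelled exploratory.
- State as a limitation that treatment triggered by the endoscopic grade can distort the comparison, including beta blockers, which are not a competing event. Tabulate treatment received by endoscopic grade.
- For 3.2.3, as a separate small addition, use the same measure without and with DECT, apply bootstrap optimism correction, and state how grade is coded. The correction is partial: in the simulation the mean corrected gain still ranged from -0.02 to +0.04 when the true gain was 0.

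The cost is SAP wording and modest programming, with no change in sample size. The data table in section 11 already tracks bleeding, intervention, TIPS, transplant and death, and sections 6 and 12 plan to record treatment of high-risk varices. The remaining downsides are wide intervals and a treatment effect that can be described but not removed.

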Study participants will undergo DECT imaging of the liver in the late arterial and in the portal venous phases. The late arterial phase will be performed with bolus tracking and occur 20 seconds after triggering. The portal venous phase will also be performed with bolus tracking and occur 40 seconds after triggering. Both phases will utilize our standard-of-care DECT image acquisition protocol. Imaging will be performed per standard of care, with the patient in the supine position with arms above the head. No oral contrast will be administered. Noncontrast and delayed phase imaging will not be performed to reduce the radiation dose.

11.3.2 DECT Image Evaluation:

The DECT images will be interpreted according to our standard of care with a dictated report by a board-certified abdominal radiologist. The radiologist interpreting the study will be asked to interpret the study using a structured reporting template that includes the grade of esophageal varices, presence or absence of other varices, presence or absence and stage of HCC, severity of ascites, and patency of liver vasculature. The structured report template is currently in use by multiple abdominal faculty and can be easily acquired by any abdominal radiologist at UAB through Powerscribe, our routine dictation reporting system.

Each DECT study will be de-identified per standard technique using OsiriX. A coded identifier will be applied to each image, and the images will be stored on OsiriX and on a secure password-restricted Server Message Block (SMB), a virtual hard drive established for Radiology Clinical Research that has restricted access to defined users. Study personnel will use the Liver Surface Nodularity (LSN) Software to measure the LSN score on all patients, while remaining blinded to the clinical data. [name] or [name] will review all of the exported images and confirm a satisfactory measurement for each patient, with revising of measurements that are not satisfactory.

11.3.3 Inter-observer Analysis:

After all patients are recruited (N=50), a designated co-investigator will set up reading session for the other radiology co-investigators (N=4 radiology residents and N=4 radiology faculty). A training video will be prepared and used to instruct the readers on how to view the images, conduct the reading sessions, and record the data in a REDCap.

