Each reader will interpret the images independently in timed reading sessions, while blinded to clinical data. The most important data point will be the grade of esophageal varices, though readers will also evaluate for presence or absence of other varices, presence or absence and stage of HCC, severity of ascites, and patency of liver vasculature.

12. 2-YEAR FOLLOW UP:

The primary purpose of screening for gastroesophageal varices is to prevent future variceal bleeding and the associated high mortality. Detection of bleeding events is therefore a critical component of the study. The patients will be contacted by phone by the study coordinator at 1- and 2-years post endoscopy to capture information on complications of cirrhosis, particularly bleeding episodes and treatment of high-risk gastroesophageal varices. If the patient has a visit to the hepatologist, the interview may alternatively be conducted at that time per patient preference. The electronic medical records will also be searched for complication of cirrhosis and bleeding episodes. The study coordinator will conduct the interviews and record all data in a REDCap database. The patients will be discharged from the study after the 2 year follow up interview.

13. STATISTICAL CONSIDERATION:

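### The inter-observer ICC uses reader experience where individual reader belongs, so it over-weights any resident-faculty gap and comes out modestly too low when one exists

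*Combined protocol and SAP*

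**What the plan says.** Objective 3.2.1 is "To assess inter-observer agreement for the detection of any varices and high-risk varices on dual energy CT". Section 11.3.3 sets up the reading study once all 50 patients are recruited, with "N=4 radiology residents and N=4 radiology faculty". On how they read: "Each reader will interpret the images independently in timed reading sessions, while blinded to clinical data".

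For the analysis, section 13.2 says: "Reader experience and subject will be the two random effects in the model used for interobserver variability". It defines the ICC as the "ratio between subject variance and the sum of variances for subject, reader experience and error term". It then attaches verbal labels to the ICC, with cut points at 0.20, 0.40, 0.60 and 0.80.

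The document has no random effect for the individual reader, does not define the levels of reader experience, and plans no separate ICC for residents and for faculty. Section 13.2 gives two-sided 95% intervals for sensitivity, specificity, accuracy and AUC, but mentions none for the ICC.

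**The concern.** Agreement between observers depends on how much individual readers differ when they look at the same scan. Here the readers are eight people, but the only reader-side term in the model is a grouping of them. Three things follow if that grouping is resident versus faculty:

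- A variance component is estimated from two levels, that is, with 1 degree of freedom.
- A systematic difference between the groups is weighted more heavily than it contributes to the variance among the eight readers.
- A reader's consistent tendency to over-call or under-call is handled as independent noise, although it recurs on every scan that the reader sees.

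At stake is the reported size of the ICC and the label attached to it. A four-plus-four reader panel makes a resident-faculty difference foreseeable, and that is when the planned ICC goes astray. The report could then not separate a training effect from general disagreement.

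**Working it through.** **Inputs from the document.** 50 patients and 8 readers in two groups of 4 (11.3.3); random effects and ICC definition (13.2). The plan states no ICC target, precision or variance component, so there is no figure of its own to reproduce.

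**Assumptions.** Experience has two levels. Every reader reads every patient, which sections 11.3.3 and 13 imply but do not state. All variance components below are assumed.

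**1. Weight given to a gap.** Place residents at −d/2 and faculty at +d/2, with no other reader differences.

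- Two-level component (planned): 2 × (d/2)² / (2 − 1) = d²/2.
- Variance among the eight readers (crossed model): 8 × (d/2)² / (8 − 1) = 2d²/7.
- Ratio: (1/2) / (2/7) = 1.75.

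**2. Where individual reader variance goes when there is no gap.** Take subject variance 0.6, reader variance 0.1 and error variance 0.3. The crossed-model target is 0.6 / (0.6 + 0.1 + 0.3) = 0.600. Under the planned model:

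- Error degrees of freedom: 400 − 1 − 49 − 1 = 349.
- Error: 0.3 + (50 × 6 × 0.1)/349 = 0.386.
- Experience: (200 × 0.1/4 + 0.3 − 0.386)/200 = 0.025.
- Subject: 0.6 + (0.3 − 0.386)/8 = 0.589.
- ICC: 0.589 / (0.589 + 0.025 + 0.386) = 0.589.

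Omitted reader variance therefore still reaches the denominator, mostly through error. Simulation (2000 runs) gives a mean of 0.586 planned against 0.597 crossed.

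**3. Effect of a gap on a continuous scale.** With subject variance 0.6, error variance 0.3 and no other reader variance:

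| Gap d | Planned: 0.6 / (0.9 + d²/2) | Crossed: 0.6 / (0.9 + 2d²/7) | Difference |
|---|---|---|---|
| 0.5 | 0.585 | 0.618 | −0.032 |
| 0.8 | 0.492 | 0.554 | −0.062 |
| 1.0 | 0.429 | 0.506 | −0.077 |

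At a gap of 0.5 the two values fall on opposite sides of the 0.60 cut point.

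**4. Binary calls, which is what objective 3.2.1 concerns.** Simulated 50 × 8 reads on an assumed latent scale: patient SD 1.5, noise SD 0.8, reader SD 0.3. The last column is the share of data sets in which planned and crossed ICCs earn different labels.

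| Gap | Planned | Crossed | Difference | Label differs |
|---|---|---|---|---|
| 0 | 0.545 | 0.547 | −0.002 | 1% |
| 1.0 | 0.458 | 0.480 | −0.022 | 11% |
| 1.5 | 0.380 | 0.416 | −0.036 | 19% |

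A separate run at gap 0.5 gave 0.520 against 0.528, a difference of −0.008. With no gap, the two-level experience component was estimated as exactly zero in about 43% of runs. A second set of assumed components gave binary differences of about 0.005 to 0.02.

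**5. Experience as a fixed effect.** If experience is fixed and the ICC keeps only subject, reader and error, the same binary scenario gives 0.509 at gap 1.0 and 0.474 at gap 1.5. Those lie +0.029 and +0.058 from the crossed values, further away than the plan's −0.022 and −0.036.

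**The case against.** The best defence is that the planned ICC works tolerably. With no gap it differs from the crossed ICC by 0.002 on binary calls, because omitted reader variance lands in the error term and error is in the denominator. This stands. A reader might infer that the plan fails to estimate agreement between readers at all; the ICC definition in 13.2 and the no-gap results do not support that.

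A reader might also infer that a resident-faculty gap is counted twice. No term enters twice. A factor of 2 appears only against d²/4, the variance in an unlimited 50:50 reader pool. The like-for-like comparison with a crossed model of these eight readers gives 1.75.

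The two-level reading is itself an inference. If experience were recorded as, say, years in practice, with a different value for each reader, the term would coincide with individual reader and the point would reduce to wording. Section 11.3.3 describes only two kinds of reader, so two levels is the natural reading, but the plan should say so.

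The sizes depend on assumed gaps. Gaps of 1.0 and 1.5 are 3.3 and 5 times the assumed reader SD of 0.3, and the plan provides a training video for all readers. A smaller gap means a smaller bias. This too stands.

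Finally, making experience a fixed effect might look like the natural cure. It removes a real source of disagreement from the denominator and answers a different question, so it is unsuitable as the main figure.

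**Conclusion.** Wrong as written, with modest impact. The model for agreement between readers has no reader term, and nothing elsewhere in the document supplies one. If experience has two levels, its variance has 1 degree of freedom, is often estimated as zero when there is no gap, and over-weights a gap by a factor of 1.75. The planned ICC is then close to correct without a gap and low by about 0.01 to 0.04 on binary calls with one. That is enough to change the label in some data sets.

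The mis-specification can be read directly from 13.2 and 11.3.3. Its size rests on the two-level reading, a fully crossed design and assumed variance components. The objective is secondary, no decision in the plan depends on the label, and the primary ROC analysis is unaffected.

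**What to change.** In section 13.2:

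- Replace reader experience with individual reader (eight levels) as a random effect crossed with subject.
- Define ICC = subject variance / (subject + reader + error variance), and state that a resident-faculty gap counts as disagreement in this overall figure.
- Report the same ICC separately within residents and within faculty, which shows the training difference directly.
- Give each ICC a confidence interval from a bootstrap over patients, noting that such an interval is conditional on these eight readers.
- State that experience means resident versus faculty, if that is intended. Show any ICC with experience as a fixed effect only as a supplementary, experience-adjusted figure.

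The cost is a few sentences. The readings, data and software are unchanged. Because the reading sessions follow completion of recruitment, the change is best made before any reads are seen, so that the model is not chosen after the fact.

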2. BACKGROUND AND RATIONALE

Cirrhosis leads to portal hypertension and development of gastroesophageal varices, which are the most common cause for bleeding in cirrhosis and a major cause of death. Bleeding varices have a 6-week mortality of 15%-25%.^{1,2} About 50% of patients with cirrhosis have varices, and 30% have large varices (>5 mm) that are high risk for bleeding.³

The American Association for the Study of Liver Disease (AASLD) recommends screening endoscopy every 2 years to evaluate for varices, and annual surveillance for those with small varices on endoscopy.⁴ Patients at a high risk of bleeding with large varices, small varices and red wale signs (an endoscopic finding), or small varices and decompensated cirrhosis proceed to treatment such as prophylactic band ligation and beta blockers.^{5,6,7} Conversely, patients with no varices or small varices (≤ 5 mm) continue surveillance efforts by endoscopy to monitor for development of large varices.^{3,7,8} Unfortunately, endoscopy is costly, requires sedation, is poorly tolerated, is subject to high inter-observer

variability, cannot detect other signs or portal hypertension or para-esophageal varices that are at risk for future bleeding events, and is associated with risks that include bleeding, esophageal injury and aspiration.⁹ Many of these factors contribute to poor patient compliance with AASLD recommendations.

Noninvasive methods for detecting, grading, and risk stratification of esophageal varices are needed. Imaging tests such as ultrasound elastography to measure liver stiffness have been proposed as a method to predict the presence of varices but have insufficient accuracy to eliminate the need for endoscopy.¹⁰ An ideal biomarker to screen for esophageal varices would be part of the routine standard of care of patients with cirrhosis, noninvasive, rapid, less expense than endoscopy, highly accurate, highly reproducible, and would require no sedation, provide a quantitative measure of the size of the varices, provide a mechanisms to assess the risk of future bleeding, allow for an assessment for other signs of portal hypertension, and provide other benefits to the patient (e.g. detect ascites and HCC and assess liver vasculature).

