4.2 Exclusion Criteria

- 4.2.1** Inability to provide written informed consent
- 4.2.2** History of bleeding gastroesophageal varices, variceal intervention or portosystemic shunt
- 4.2.3** Prior liver transplant
- 4.2.4** History of malignancy
- 4.2.5** Severe chronic kidney disease with estimated glomerular filtration rate (GFR) < 30 mL/min/1.73 m²
- 4.2.6** Presence of acute kidney injury
- 4.2.7** Prior iodinated contrast allergy
- 4.2.8** Patient weight >300 lbs
- 4.2.9** Multiphasic liver CT within 3 months of upper endoscopy
- 4.2.10** Pregnancy

4.3 Inclusion of all races and ethnic groups are eligible for this trial. There is no bias towards age or race in this trial. The trial is open the accrual of women and men.

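### Endoscopic grade helps trigger the prophylaxis that prevents the bleed, so on most scales the planned comparison of endoscopic and DECT grade for 2-year variceal bleeding is tilted toward DECT

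*Combined protocol and SAP*

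**What the plan says.** - **Objective.** Section 3.2.2: "To compare the accuracy of grade of varices on CT to grade of varices on endoscopy for predicting gastroesophageal variceal bleeding at 2 years". Objective 3.2.3 adds models of 2-year bleeding risk without and with DECT findings.
- **What follows a high-risk finding.** Section 2 says that patients with large varices, small varices with red wale signs (which it identifies as an endoscopic finding), or "small varices and decompensated cirrhosis proceed to treatment such as prophylactic band ligation and beta blockers". The remaining patients "continue surveillance efforts by endoscopy to monitor for development of large varices".
- **Entry.** Section 4.2 excludes "History of bleeding gastroesophageal varices, variceal intervention or portosystemic shunt". Any variceal intervention in the cohort therefore falls at or after the index endoscopy.
- **Analysis.** Section 13.2 plans Cox models for time to bleeding, then "Cause specific proportional subhazards analysis" while "accounting for competing risks (e.g. gastroesophageal banding) and adjusting for covariates", and later cumulative incidence functions with attention to 2-year bleeding. The only analysis labelled for Aim 2.2 is a weighted kappa between the two grades, which does not measure prediction of bleeding.
- **Treatment data.** Sections 6 and 12 collect variceal treatment at 1 and 2 years. Section 13.2 uses it only through the banding example, and beta blockers do not appear there.
- **Composite.** The table of clinical data in section 11 lists intervention for varices among the liver-related events.

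**The concern.** Two tests are to be ranked on an outcome that one of them helps to change. A high endoscopic grade leads to treatment, and treatment removes bleeds mainly from patients whom endoscopy called high risk. Endoscopy then looks like a weaker predictor because acting on it worked. DECT loses fewer of its high-grade bleeds, because the two tests do not always agree.

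Treating banding as a competing event can add to this: a bleed after banding is no longer counted, and the uncounted bleeds again sit mainly in endoscopic grade 2. At stake is a false signal that DECT predicts bleeding better than endoscopy. Section 13.2 says of the related Aim 2.4 that a trend could justify further work, so even a weak signal in that direction may be acted on.

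**Working it through.** **The plan's own figure.** Section 13.1 states more than 95% power for the primary AUC (0.90 against 0.5; 34 patients with varices, 16 without; one-sided 0.05). Hanley–McNeil gives SE 0.0429 at AUC 0.90. The null SE is √(51/(12×34×16)) = 0.0884, so z = (0.40 − 1.645×0.0884)/0.0429 = 5.9 and power exceeds 99.9%. That agrees with the plan but does not concern bleeding. The documents give no bleeding rate, treatment rate or event count for the bleeding comparison, so those inputs are assumed below.

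**Inputs.** Grade mix 32/32/36% (section 13.1). Assumed: untreated 2-year bleeding 2/10/30% by true grade; each test gives the true grade with probability 0.8 and otherwise an adjacent grade, with errors independent given the true grade; every endoscopic grade 2 patient is treated early.

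**Step 1: untreated.** Bleeding fractions by endoscopic grade:
- Grade 0: 0.32×0.8×0.02 + 0.32×0.1×0.10 = 0.0083
- Grade 1: 0.32×0.2×0.02 + 0.32×0.8×0.10 + 0.36×0.2×0.30 = 0.0485
- Grade 2: 0.32×0.1×0.10 + 0.36×0.8×0.30 = 0.0896

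The total is 0.1464, or 7.3 bleeds in 50. Patients fall 0.288/0.392/0.320 by grade. DECT has the same table.

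With b and n the grade shares among bleeders and non-bleeders, AUC = b2(n0+n1+n2/2) + b1(n0+n1/2) + b0·n0/2 = 0.714 for both tests.

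**Step 2: where the prevented bleeds sit.** All 0.0896 are endoscopic grade 2. By DECT grade they split 0.0003/0.0198/0.0694, so DECT loses only 0.0694/0.0896 = 78% of them from its own top grade.

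**Step 3: apply treatment.**

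| Scenario | Bleeds by endoscopic grade | Bleeds by DECT grade | AUC endoscopy | AUC DECT | Bleeds in 50 |
|---|---|---|---|---|---|
| No effect | .0083/.0485/.0896 | .0083/.0485/.0896 | 0.714 | 0.714 | 7.3 |
| Risk halved | .0083/.0485/.0448 | .0082/.0386/.0549 | 0.626 | 0.666 | 5.1 |
| Post-banding bleeds not counted | .0083/.0485/0 | .0080/.0286/.0202 | 0.430 | 0.566 | 2.8 |

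Simulated trials of 50 patients put DECT ahead in about 65% (risk halved) and 83% (not counted), against 50% with no treatment effect. Untreated bleeding of 1/5/15% gives 0.619 against 0.657 and 0.432 against 0.564.

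**Step 4: dependence on the model.** Simulation of 40,000 patients per scenario, 80% of endoscopic grade 2 banded early. Hazard ratios are grade 2 against lower, endoscopy then DECT; small untreated differences are Monte Carlo noise.

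| Scale | Untreated | 80% banded |
|---|---|---|
| 2-year AUC | 0.71, 0.71 | 0.55, 0.63 |
| Subdistribution HR | 3.59, 3.73 | 0.84, 1.98 |
| Cause-specific HR, both grades in one model | 2.11, 2.34 | 1.82, 3.38 |
| Cause-specific HR, one test at a time | 3.59, 3.73 | 3.90, 4.32 |

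A beta-blocker-type treatment (assumed HR 0.5, given to 80%, not a competing event) gives single-test HRs of 2.24 and 2.94.

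**Step 5: untreated patients only.** If all endoscopic grade 2 are treated, 50×0.680 = 34 patients and 2.8 bleeds remain, none with endoscopic grade 2. AUC is 0.651 for endoscopy and 0.705 for DECT (0.65 and 0.71 by simulation). With 80% treated it is 0.69 and 0.72.

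**The case against.** **The wording does not fix the model.** The phrase in 13.2 mixes cause-specific and subdistribution terms. If it means single-test cause-specific models that censor at banding, endoscopy's hazard ratio hardly moves (3.59 to 3.90). This stands, and a reader who infers that the plan favours DECT under any analysis goes too far. But objective 3.2.2 asks about accuracy at 2 years and 13.2 also plans cumulative incidence; on those scales the tilt is large.

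**Endoscopy may not be the only trigger.** DECT follows within two weeks (section 6), its report carries a variceal grade (11.3.2) and it enters the medical record (8.5). If grade 2 on either test leads to banding in 80%, AUC is 0.57 for both. Decompensation is also a listed trigger. These points shrink the asymmetry. Section 2 nonetheless describes treatment in terms of variceal size and red wale signs, the latter expressly endoscopic.

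**Objective 3.2.4.** It is tempting to extend the point to all liver-related events. The documents do not support that: variceal intervention is itself such an event, so for that composite the bias may run toward endoscopy.

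**Consequence.** These are secondary aims in a 50-patient pilot with few bleeds, so a firm superiority claim is unlikely. That limits the weight of the point, but imprecision does not remove a directional bias.

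**Conclusion.** The concern holds for the bleeding endpoint under 3.2.2 and 3.2.3. With two equally accurate tests, AUC moves from 0.71 for both to about 0.63 against 0.67 if treatment halves the risk (simulation gives 0.62 to 0.63 for endoscopy), and to 0.43 against 0.57 if post-banding bleeds are dropped. These sizes rest on assumed bleeding, accuracy and treatment rates, and on endoscopy being the main driver of treatment. The direction follows from sections 2, 3.2, 4.2 and 13.2.

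Two further inferences are not supported. The primary AUROC is not compromised, because it compares DECT with endoscopy at baseline and does not use bleeding. Nor would moving the head-to-head to untreated patients cure the problem: it selects on endoscopic grade and still favours DECT. About 3 to 5 bleeds in 50 are expected under these inputs with all endoscopic grade 2 treated, so the results will be imprecise whatever model is used. This is a cheap improvement to the plan.

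**What to change.** Amend section 13.2 as follows.

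1. For the bleeding endpoint, keep patients at risk after banding and count their bleeds. Limit competing events to those that end the risk, such as death or transplant, and name the hazard model. This reduces the bias but does not remove it; the risk-halved row shows what can remain.
2. State that the comparison describes prediction under endoscopy-guided care and will not support a claim that DECT predicts bleeding better than endoscopy.
3. Report results by treatment received, including beta blockers, only as a descriptive sensitivity analysis and not as the head-to-head.

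The change costs SAP wording and one descriptive analysis of the treatment data already planned for 1 and 2 years. No patient procedure changes. The downside is a narrower conclusion.
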